### **5.8 Duration of Therapy**

In the absence of treatment delays due to adverse events, treatment may continue until completion or protocol-defined therapy or until:

- Disease progression
- Inter-current illness that prevents further administration of therapy
- Unacceptable adverse events
- Patient decided to withdraw from the study
- General or specific examples in the patient's condition render the patient unacceptable for further treatment in the judgement of the investigator

Subjects who become medically incapacitated or cognitively impaired after enrollment into this trial may continue with protocol therapy as long as they are benefiting from treatment in the judgement of the investigator. In the event that this occurs, a surrogate or legally authorized representative (LAR) must sign the ICF. The surrogate/LAR will assist the subject in completion of study procedures and diary. If a subject regains ability to regains the cognitive ability to consent, they must be re-consented using standard consenting procedure

## **5.9 Duration of Follow Up**

Patients will be followed every 3 months for one year after removal from or completion of treatment or death, whichever comes first. Patients removed from treatment for unacceptable adverse events will be followed until resolution or stabilization of the adverse event then for relapse and survival afterwards. Patients who undergo allogeneic stem cell transplant will only be followed for survival.

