**SCHEDULE OF EVENTS**

Protocol Activity	Screening	Induction/ Re-induction E (Days 1-75)							Consolidation J (Days 1-55)				Maintenance K (Days 1-28)	EOT	Follow-up
	≤ 28 days prior to D1	D1	D3	D5	D6	Weekly (+/- 2 days)	Induction response D20 (+1 day)	Remission evaluation D28 to D60	D1	D3	D4	Weekly (+/- 2 days)	D1 (+/- 7 days)	Within 7 days of last dose	Every 3 month (+/- 14 days)
Informed Consent A	X														
Clinical Evaluation and Procedures															
Eligibility Review	X														
Disease Classification	X														
Medical History	X														
Concomitant Medication Review	X	For the entire duration of study participation													
AE/ SAE Review		From when participant start study therapy on induction day 1 up until 28 days after the last dose of study therapy/ and until resolution of any treatment-related AE/ SAE													
Physical Exam	X	X				X			X			X	X	X	X
ECOG Performance	X	X				X			X			X	X	X	X
12-lead ECG	X				X G	X G,H					X G			X	
ECHO	X														
BMA/BMBX	X C						X	X				X N		X L	
MRD (send to UW)							X	X						X L	
Cytogenetics /Molecular profiling	X C						X	X						X L	

Research sample for gene expression correlatives	X C, D						X D	X D						X D,L	
HSCT information/ Survival Status															X M
Laboratory Assessments															
Hematology	X	X				X	X	X	X			X	X	X	X
Chemistry	X	X				X			X			X	X	X	
Urinalysis	X														
Coagulation	X														
Pregnancy Test B	X								X				X		
Study treatment															
CPX-351 Infusion		X	X	X F					X	X					
Glasdegib					X I						X I		X		

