### 2.1 Primary Objective/ Primary Endpoint

2.1.1 Primary Objective	2.1.2 Primary Endpoint

 
To determine the efficacy when using the combination of CPX-351 and Glasdegib to treat patients with newly diagnosed AML with MDS-related changes or treatment related AML
 
	
 
Efficacy will be measured by following the 6 month event-free survival (EFS). EFS is defined as the as the time from screening biopsy to the date of confirmed disease progression, relapse from CR/CRi, treatment failure, or death, whichever comes first. Of interest, a 6 month EFS will be important to follow
 

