### **7.2.5 Assessment of remission status**

The date of CR and CRi or relapse is based on the date of the bone marrow biopsy that was performed. The exact date of achievement of CR is based on the date when the bone marrow biopsy demonstrates less than 5% blasts with the peripheral ANC  $\geq 1,000/\mu\text{L}$  and the platelet count  $\geq 100,000/\mu\text{L}$ . If the bone marrow biopsy shows less than 5% blasts prior the day the peripheral counts recover, then the date of CR is based on the date when the peripheral counts recover.

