### **7.2.7 Consolidation**

- Physical exam will be done weekly
- Review of concomitant medications
- Adverse event assessment
- Blood draws for laboratory studies will be done weekly
- For females with childbearing potential, a pregnancy test will be done
- ECOG performance status
- ECGs will be done on within 24 hours of day 4 of every cycle
- Adverse event assessment
- Bone marrow at the end of consolidation is recommended but is not required by the study.

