## **10.4 Event-free survival**

Event-free survival is defined as the time from screening biopsy to the date of confirmed disease progression, relapse from CR/CRi, treatment failure, or death, whichever comes first. This was chosen as an endpoint for several reasons. It is known to incorporate several endpoints of interest including efficacy of the treatment as well as toxicity that both contribute to the outcome of the patient. Complete remission may not capture the full benefits of Glasdegib since the drug may prevent relapse through different mechanisms than enhanced cytotoxicity.

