### **13.2 Data Analyses Plans**

#### **13.2.1 Primary Objectives**

For efficacy, the primary objective is to estimate proportion of evaluable participants who are event-free at six months (EFS6) and compare to the historical figure of 50 percent.

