### 13.2.2 Primary Endpoint

The primary endpoint for efficacy is EFS6. The event-free interval begins with the date of diagnostic biopsy, and ends as described in Section 2.1.

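### No disease check is tied to month 6, so a few relapses before month 6 in patients already off treatment can be dated after it and scored event-free; the effect is small and one-directional

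*Combined protocol and SAP*

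**What the plan says.** Section 13.2.1 sets the primary objective: to "estimate proportion of evaluable participants who are event-free at six months (EFS6) and compare to the historical figure of 50 percent". The clock is fixed to the biopsy. Section 13.2.2 says "The event-free interval begins with the date of diagnostic biopsy, and ends as described in Section 2.1", while section 10.4 says "Event-free survival is defined as the time from screening biopsy to the date of confirmed disease progression, relapse from CR/CRi, treatment failure, or death". The plan therefore speaks of a diagnostic biopsy in one place and a screening biopsy in the other, but both precede treatment and neither depends on when treatment stops.

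Follow-up runs on a different clock. Section 5.9 states "Patients will be followed every 3 months for one year after removal from or completion of treatment or death". Section 7.4 repeats this, and the Schedule of Events gives each visit a window of 14 days either way. Exam and hematology are listed at these visits. Marrow is done only when relapse is suspected, at the physician's discretion (7.4).

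Section 7.2.5 dates the event: "The date of CR and CRi or relapse is based on the date of the bone marrow biopsy that was performed". Section 7.2.7 adds "Bone marrow at the end of consolidation is recommended but is not required by the study".

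Patients still on treatment are seen weekly in induction and consolidation, and monthly in maintenance (Schedule; 5.7). Transplanted patients are followed for survival only (5.9, 7.4). No section sets a month-6 assessment or says how to score a relapse first found after month 6.

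**The concern.** A fixed-time proportion is only as good as the observation of status at that time. A patient in remission who stops early without transplant, for toxicity, intercurrent illness or choice (5.8), leaves weekly or monthly review for three-monthly review. Suppose treatment stops at month 3.5. The nominal visits are then at months 6.5 and 9.5. A relapse at month 5 that causes no symptoms is found at about month 6.5, biopsied then and dated then, and EFS6 counts the patient as event-free.

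Late detection can move an event only from before month 6 to after it, so observed EFS6 can be raised but not lowered. What is at stake is a go/no-go rule that a single patient can tip.

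**Working it through.** **Decision rule (13.2.3, 13.3).** The regimen passes if the exact one-sided 90% lower bound exceeds 0.5. The bound for x event-free of n is the 10th percentile of Beta(x, n − x + 1).

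- The plan's table gives 51% for n = 28 and 65%. At the expected count of 0.65 × 28 = 18.2 the formula gives 0.511, which agrees.
- n = 28: 18 event-free gives 0.504 (pass); 17 gives 0.468 (fail). P(X ≥ 18 | 0.50) = 0.092.
- n = 30: 20 gives 0.534 (pass); 19 gives 0.49987 (fail). P(X ≥ 20 | 0.50) = 0.049.

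Section 13.3 also claims at least 90% probability of passing at 65% with 28 patients. The exact figure is 61.6%. That is a separate matter, and this point does not depend on it.

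**When the gap opens.** Take month 6 as 183 days and three months as 91 days.

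- Biopsy on day 1: 183 − 91 = 92. A patient who stops after about day 92 has no nominal follow-up visit before month 6.
- Biopsy 28 days before day 1 (allowed by Schedule footnote C): 183 − 28 = 155, and 155 − 91 = 64. The cut-off is about day 64.
- The 14-day window can move either cut-off by two weeks.

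**Share misdated among early stoppers.** Assumptions: stopping time s is uniform between months 2 and 5 from the biopsy; time from stopping to relapse is exponential with median 6.9 months (the remission duration on CPX-351 in section 1.5.3, treated as a median); detection occurs only at nominal visits, 3 and 6 months after stopping. The rate is λ = ln 2 / 6.9 = 0.1005 per month.

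- Relapse before month 6: 1 − (e^(−λ) − e^(−4λ))/(3λ) = 1 − 0.781 = 0.219.
- Stop in months 2–3 (a visit falls before month 6, so only later relapses are missed): e^(−3λ) minus the mean of e^(−λu) over u = 3 to 4 = 0.740 − 0.704 = 0.036.
- Stop in months 3–4: 1 minus the mean over u = 2 to 3 = 1 − 0.778 = 0.222.
- Stop in months 4–5: 1 minus the mean over u = 1 to 2 = 1 − 0.860 = 0.140.
- Average: (0.036 + 0.222 + 0.140)/3 = 0.132, or 0.132/0.219 = 60% of the relapses before month 6.

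**How many patients.** The documents give no figure. Section 1.5.3 cites 47% CR/CRi and 34% transplanted on CPX-351. If both applied to all 28 patients, 0.47 × 28 = 13.2 would remit and 0.34 × 28 = 9.5 would be transplanted, leaving about 4 non-transplanted remitters. Some of these would be on monthly-reviewed maintenance. I therefore assume 1 to 3 early stoppers.

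**Effect on EFS6.**

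| Early stoppers (assumed) | Patients misdated (× 0.132) | Points of EFS6, n = 28 | Points, n = 30 |
|---|---|---|---|
| 1 | 0.13 | 0.5 | 0.4 |
| 2 | 0.26 | 0.9 | 0.9 |
| 3 | 0.40 | 1.4 | 1.3 |

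If half of these relapses come to light earlier through symptoms, the n = 28 range becomes about 0.2 to 0.7 points.

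**Effect on the false-positive rate.** With true EFS6 at 50% and an upward shift of 1 point, P(X ≥ 18 | 28, 0.51) = 0.111 against 0.092, and P(X ≥ 20 | 30, 0.51) = 0.062 against 0.049.

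**The case against.** The best case against acting is that this is ordinary interval observation in a handful of patients, and that the plan already has several routes to earlier detection. There is an end-of-treatment exam and hematology within 7 days of the last dose. Marrow may be done whenever relapse is suspected. Patients removed for unacceptable adverse events are followed until the event resolves or stabilises, and then for relapse (5.9, 7.4). A stop shortly after month 3 can still have its first visit before month 6 through the 14-day window. All of this stands, and it is why the estimate is small.

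A reader might infer something stronger: that every relapse before month 6 is dated late once treatment stops after month 3, that nothing else closes the gap, and that EFS6 is inflated by several points. The routes just listed contradict the first two. The third would need 4 to 8 early stoppers (4 × 0.132/28 = 1.9 points; 8 × 0.132/28 = 3.8 points), which equals or exceeds the whole pool of about 4 non-transplanted remitters implied by the rates in section 1.5.3.

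It can also be said that the comparison with the historical 50% is unaffected if that figure came from a similar visit schedule. Part of the bias would then cancel. The documents do not describe that schedule, so this can be neither claimed nor excluded.

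What survives is the mechanism. None of the existing routes guarantees a disease check near month 6 in a patient without symptoms, and no scoring rule covers a relapse found just after it.

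**Conclusion.** The point holds as a small, one-directional misclassification of the primary endpoint. Observed EFS6 can be raised by about 0.5 to 1.4 points, or about half that with symptom-led detection. This rests on an assumed 1 to 3 early stoppers in remission, the assumed stopping and relapse distributions, and the remission duration from section 1.5.3 carried over to this regimen. The expected error is well under one patient, so it does not by itself undermine the trial's conclusion. It is worth removing because adjacent counts give opposite decisions at both 28 and 30 patients, and because the remedy uses a visit that is already planned.

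**What to change.** **Sections 5.9, 7.4 and Schedule of Events.** For each non-transplanted patient who is off treatment and event-free, move the nearest three-monthly visit to month 6 from the EFS start date, with a narrow window, for example day 183 ± 7. Content stays as listed: exam and CBC with differential, with marrow only on suspicion. A wide window would work against the purpose: at ± 14 days, a check on day 169 leaves two weeks unobserved, and one on day 197 can pick up relapses that arose after month 6.

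**Section 13.2.2.** Score a relapse first suspected at that check as an event by month 6, even if the confirming marrow falls a few days later. Add a sensitivity analysis that counts any relapse found at the first assessment after month 6 as an event by month 6. Use one name for the EFS start date, since the month-6 visit is counted from it.

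**Cost.** Wording changes only, with no added visit or biopsy. A few patients will have a slightly irregular visit interval, a relapse arising within days after month 6 may be counted, and EFS6 may come out slightly lower.

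**Not covered.** This change does not capture relapse in transplanted patients, who have survival follow-up only. That gap needs its own rule.

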## **5.10 Other therapeutic Agents**

The use of therapeutic agents or approaches for malignancy outside of what is expressly stated in this protocol is strictly forbidden. This includes any study undefined use of the study specific therapeutic agents, the same class of agents, or agents not expressly defined in the protocol with potential or known anti-leukemic activity. Institutional standard of care supportive medications are allowed as long as they do not have known or predicted anti-leukemic activity or are in conflict with study dictated supportive care.

If hyperleukocytosis is present (when greater than 30k), cytoreduction is allowed with leukapheresis, corticosteroids or hydroxyurea for up to 7 days at the investigator's discretion.

## **5.11 Pre-Medications**

Anti-emetics should be given prior to CPX-351. The exact antiemetic should be used per the institutional protocol or treating physician discretion. One common regimen is ondansetron 8mg IV on days 1, 3 and 5 given 30 minutes prior to CPX-351 administration. Monitor for infusion reactions during and at least 1 hour after the end of the infusion.

## **5.12 Infection prophylaxis**

### **5.12.1 Prophylaxis during neutropenia**

Prophylaxis during neutropenia including antibacterial and antifungal therapies is to be administered per local standard of care. For antibacterial prophylaxis, levofloxacin 500mg daily is recommended. Cefpodoxime is an allowable alternative to avoid QTc prolongation. Acyclovir is strongly recommended for viral prophylaxis.

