### 5.1 Treatment Dosage and Administration

Agent	Dose	Route	Schedule
CPX-351 for Induction	Daunorubicin 44mg/m  -cytarabine 100mg/m 	IV infusion for 90 minutes	Days 1, 3 and 5
CPX-351 for Reinduction	Daunorubicin 44mg/m  -cytarabine 100mg/m 	IV infusion for 90 minutes	Days 1 and 3
CPX-351 for Consolidation	Daunorubicin 29mg/m  -cytarabine 65mg/m 	IV infusion for 90 minutes	Days 1 and 3
Glasdegib	100 mg	PO daily in the a.m.	Begins day after completion of CPX-351 infusion and continues daily until Day 1 of subsequent cycle of CPX-351

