#### **5.14 Prohibited concomitant therapy**

Antineoplastic agents other than CPX-351, Glasdegib and hydroxyurea prior to the start of the study are not allowed.

Glasdegib can lead to QTc prolongation. Therefore, drugs that can prolong QTc should be avoided. Please refer to list of drugs in Appendix D.

Caution must be taken with moderate/strong CYP3A4/5 inhibitor in conjunction with Glasdegib. If possible, it is best to avoid the combination. If this is not possible, then QTc monitoring is recommended.

When there is an urgent need to start a moderate/strong CYP3A4/5 inhibitor or TdP drug, administration of these medications should not be delayed, the Investigator should consider temporarily interrupting Glasdegib dosing and should implement these additional monitoring procedures as soon as it is reasonably possible.

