**Appendix D. Drugs known to prolong QTc**

Drugs that have known risk for QT prolongation			
Generic Name	Drug Class	Therapeutic Use	Route
Amiodarone	Anti-arrhythmic	Abnormal heart rhythm	oral, injection
Anagrelide	Phosphodiesterase 3 inhibitor	Thrombocythemia	oral
Arsenic trioxide	Anti-cancer	Leukemia	injection
Azithromycin	Antibiotic	Bacterial infection	oral, injection
Chloroquine	Anti-malarial	Malaria infection	oral
Chlorpromazine	Anti-psychotic /Anti-emetic	Schizophrenia/nausea	oral, injection
Cilostazol	Phosphodiesterase 3 inhibitor	Intermittent claudication	oral
Ciprofloxacin	Antibiotic	Bacterial Infection	oral, injection
Citalopram	Anti-depressant, SSRI	Depression	oral
Clarithromycin	Antibiotic	Bacterial infection	oral
Disopyramide	Anti-arrhythmic	Abnormal heart rhythm	oral
Dofetilide	Anti-arrhythmic	Abnormal heart rhythm	oral
Donepezil	Cholinesterase inhibitor	Dementia	oral
Dronedarone	Anti-arrhythmic	Atrial Fibrillation	oral
Droperidol	Anti-psychotic / Anti-emetic Anesthesia	adjunct, nausea	injection
Erythromycin	Antibiotic	Bacterial infection; increase GI motility	oral, injection
Escitalopram	Anti-depressant, SSRI	Major depression/ Anxiety Disorders	oral
Flecainide	Anti-arrhythmic	Abnormal heart rhythm	oral
Fluconazole	Anti-fungal	Fungal infection	oral, injection
Halofantrine	Anti-malarial	Malaria infection	oral
Haloperidol	Anti-psychotic	Schizophrenia, agitation	oral, injection
Ibutilide	Anti-arrhythmic	Abnormal heart rhythm	injection
Levofloxacin	Antibiotic	Bacterial infection	oral, injection
Methadone	Opiate	Pain control, narcotic dependence	oral, injection
Moxifloxacin	Antibiotic	Bacterial infection	oral, injection
Ondansetron	Anti-emetic	Nausea, vomiting	oral, injection
Pentamidine	Antibiotic	Pneumocystis pneumonia	injection, inhaled
Pimozide	Anti-psychotic	Tourette's tics	oral
Propofol	Anesthetic	Anesthesia	injection

Quinidine	Anti-arrhythmic	Abnormal heart rhythm	oral, injection
Sevoflurane	Anesthetic, general	Anesthesia	inhaled
Sotalol	Anti-arrhythmic	Abnormal heart rhythm	oral
Thioridazine	Anti-psychotic	Schizophrenia	oral
Vandetanib	Anti-cancer	Thyroid cancer	oral

Source: Credible Meds.org (<http://crediblemeds.org/healthcare-providers/drug-list/?rf=All>). TdP risk category filtered on Drugs with known TdP risk. Assessed 11 October 2015.

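### Section 5.12.1 recommends levofloxacin during neutropenia, section 5.14 and Appendix D say to avoid it with glasdegib, and no ECG is specified for that routine use

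*Combined protocol and SAP*

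**What the plan says.** On prophylaxis, section 5.12.1 begins: "Prophylaxis during neutropenia including antibacterial and antifungal therapies is to be administered per local standard of care". It then makes a specific recommendation, "For antibacterial prophylaxis, levofloxacin 500mg daily is recommended", and follows it with "Cefpodoxime is an allowable alternative to avoid QTc prolongation".

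On co-medication, section 5.14 notes that glasdegib can prolong QTc and continues: "Therefore, drugs that can prolong QTc should be avoided". It refers to Appendix D, whose table is headed "Drugs that have known risk for QT prolongation" and includes levofloxacin.

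Section 5.14 has two softer provisions. For moderate or strong CYP3A4/5 inhibitors, which are best avoided, it adds: "If this is not possible, then QTc monitoring is recommended". A separate clause opens "When there is an urgent need to start a moderate/strong CYP3A4/5 inhibitor or TdP drug". It says such a drug should not be delayed, that interrupting glasdegib should be considered, and that the additional monitoring should be put in place as soon as reasonably possible.

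Section 5.1 gives the glasdegib schedule: "Begins day after completion of CPX-351 infusion and continues daily until Day 1 of subsequent cycle of CPX-351". In induction the first dose is on day 6 (5.2).

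**The concern.** A site that follows the recommendation in 5.12.1 gives a patient on glasdegib a drug that 5.14 says to avoid. No written exception permits it, and no ECG is specified for it. The protocol does not say which section prevails.

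What is at stake is cardiac safety and consistency between sites. Section 14.5.15 places the study at risk level 1 because the toxicity of this combination is not well established. Under 6.4, a QTc above 500 ms interrupts glasdegib and restarts it at 50 mg, so avoidable prolongation could also reduce exposure to the study drug. The documents give no rate for either outcome.

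**Working it through.** No power or sample-size arithmetic applies. The check sets the provisions side by side and counts the listed ECGs.

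**1. Do the two drugs overlap?** In induction, glasdegib is taken daily from day 6 until the next CPX-351 cycle (5.1, 5.2). Section 7.2.1 expects cytopenias to recover around day 28 to 60. Prophylaxis given during neutropenia therefore coincides with glasdegib. For consolidation the documents give no neutropenia duration and no levofloxacin use, so overlap there is possible but not shown.

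**2. Does 5.14 reach levofloxacin?** Yes, through Appendix D. The source note to that appendix says the list was filtered on known TdP risk, so levofloxacin also counts as a TdP drug for the urgent-need clause.

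**3. Does 5.14 permit routine prophylaxis?** No. The urgent-need clause does not describe planned daily prophylaxis. The sentence recommending QTc monitoring belongs to the CYP3A4/5 inhibitor text. Neither provision gives an ECG day or frequency.

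**4. Which listed ECGs fall after the first glasdegib dose of a cycle?** The end-of-treatment ECG is left aside.

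| Phase | Listed ECGs | After that cycle's first glasdegib dose |
|---|---|---|
| Induction (7.2.1) | Day 6 pre-dose; day 13-15 | 1 |
| Re-induction (7.2.6) | Within 24 hours of day 4, pre-dose | 0 by 7.2.6; the schedule is ambiguous |
| Consolidation, up to 2 cycles (7.2.7, footnote G) | Around day 4, pre-dose | 0 per cycle |

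The re-induction entry is qualified because the Schedule of Events puts the weekly ECG in a column shared by induction and re-induction. Footnote H says that it applies during induction, and this could be read either way.

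**5. When does the induction ECG cover the combination?** It falls 13 - 6 = 7 to 15 - 6 = 9 days after glasdegib starts. A check about one week into co-administration is therefore already met if levofloxacin is running by about day 6 to 8 (6 + 7 = 13; 8 + 7 = 15). The documents do not give a levofloxacin start day, so this is an assumption. If the day 13-15 ECG is unremarkable, footnote H leaves further ECGs to the investigator. A later start then has no required ECG on the combination within that cycle.

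**6. Does 6.4 close the gap?** Only after an ECG has shown a QTc of 480 ms or more. It does not require the ECG that would find it.

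**The case against.** The strongest reply is that the authors saw the risk and dealt with it where the choice is made. Section 5.12.1 is the specific provision on prophylaxis, defers to local practice and names a QTc-sparing alternative. A site that uses cefpodoxime complies with both sections. Other safeguards are in place: exclusion of QTcF above 450 ms, ECGs on day 6 and day 13-15, discretionary ECGs, weekly chemistry including electrolytes and magnesium, and the medication review against Appendix D in 6.4. In induction, where overlap is best supported, the existing ECG may already do the job.

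Most of this stands, and it limits the size of the point. It does not remove the conflict. Cefpodoxime is only allowable, while the drug on the avoid list is the one recommended, and no rule says when to switch.

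Three stronger readings are tempting but not supported:

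- **That nothing in the protocol monitors the combination.** The day 13-15 ECG may catch it, and the urgent-need clause in 5.14 does extend monitoring to TdP drugs. The gap is confined to routine prophylaxis.
- **That re-induction and consolidation certainly leave exposed patients unmonitored.** The re-induction schedule is ambiguous, and levofloxacin exposure in consolidation is not shown. The day 4 consolidation ECG also normally precedes a restart of glasdegib, not a first exposure.
- **That levofloxacin should be barred.** The documents do not compare the agents' protection against infection. Section 1.5.3 reports more grade 3-4 infections with CPX-351 in the phase II trial but similar grade 3-5 rates in the phase 3 trial. A blanket switch would be a clinical trade-off that the plan does not inform.

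**Conclusion.** The point holds as an inconsistency between two safety provisions that should be corrected. Section 5.12.1 recommends a drug that 5.14, through Appendix D, says to avoid with glasdegib, and no ECG is specified for that routine use.

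Its size can be given only as a monitoring count: one listed ECG after the glasdegib start in induction, none in 7.2.6 for re-induction (subject to the shared column), and none in either consolidation cycle. The last matters only for a patient who is neutropenic and on levofloxacin. Patient risk cannot be estimated, because the documents give no levofloxacin uptake, neutropenia duration or QTc event rate.

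A reader might infer that the efficacy result is compromised. The documents do not support that: EFS6, the sample size and the decision rule do not depend on this provision.

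**What to change.** Add to 5.14 a written exception for levofloxacin prophylaxis under 5.12.1. Make it conditional on an ECG about one week after co-administration with glasdegib begins, in whichever cycle that occurs. An ECG already scheduled counts if it falls at that time. Section 6.4 then applies. The one-week interval is borrowed from the plan's own induction schedule and is not derived from levofloxacin data.

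State in 5.12.1 that, while the patient is on glasdegib, cefpodoxime or another agent outside Appendix D is preferred where local standard of care and infection risk allow. The exception with its ECG is the essential part; the preference is a clinical judgement for the investigators.

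The cost is two or three sentences of protocol text and an occasional extra ECG, mainly for later levofloxacin starts and for re-induction or consolidation. Antibacterial cover may differ where a site changes agent, which is why levofloxacin stays available.
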